9.3.1.3. Time to treatment discontinuation (TTD)

TTD is defined as the time from the start of treatment with avelumab plus axitinib to the end of treatment due to any cause except the effectiveness of the treatment.

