#### 3.2 STATISTICAL DECISION RULES

A two-sided 95% confidence interval will be calculated for interval estimation. In addition, no multiplicity adjustment will be performed.

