*Study 01-Jun-2020*  
 Page 8 of 30

	record of death, the date when the survival of the patient was last confirmed on record (date of last hospital visit) will be used for censoring.
Time to treatment discontinuation (TTD) of avelumab plus axitinib combination therapy as first-line therapy	Defined as the period from the date of initiation of avelumab plus axitinib combination therapy to the date of ending treatment* for any reason (excluding discontinuation due to efficacy). In the case of discontinuation due to efficacy, the date of last administration will be used for censoring. If treatment has not ended, the date of the last hospital visit will be used for censoring. * The end date of treatment is the date of last avelumab administration + 13 days or the date of last axitinib administration, whichever occurs later, or the data-cut date, if performed earlier.
TTD of avelumab as first-line therapy	Defined as the period from the date of initiation of avelumab to the date of ending administration* for any reason (excluding discontinuation due to efficacy). In the case of discontinuation due to efficacy, the date of the last avelumab administration will be used for censoring. If treatment has not ended, the date of the last hospital visit will be used for censoring. * The end date of avelumab therapy is the date of the last avelumab administration + 13 days or the data-cut date, whichever occurs earlier.
TTD of axitinib as first-line therapy	Defined as the period from the date of initiation of axitinib to the date of ending administration* for any reason (excluding discontinuation due to efficacy). In the case of discontinuation due to efficacy, the date of the last axitinib administration will be used for censoring. If treatment has not ended, the date of the last hospital visit will be used for censoring. * The end date of axitinib is the date of the last axitinib administration.
Reasons for the TTD event	Reasons for TTD event are defined as follows: Disease progression/adverse event/other (death)/other (excluding death)
Reasons for censoring TTD	Reasons for censoring TTD are defined as follows: "Treatment ongoing" will be selected if the treatment is ongoing.

PFIZER CONFIDENTIAL

CT24-WI-GL03-RF03 2.0 *Non-Interventional Statistical Analysis Plan For Secondary Data Collection*  
 Study 01-Jun-2020  
 Page 9 of 30

	" discontinuation due to efficacy " will be selected in case of discontinuation due to efficacy.
--	--

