#### 7.2.2.6 Time to treatment discontinuation (TTD) of avelumab plus axitinib combination therapy as first-line therapy

Source : Efficacy analysis set  
 population  
 Endpoints : TTD of avelumab plus axitinib combination therapy as first-line therapy  
     TTD of avelumab as first-line therapy  
     TTD of axitinib as first-line therapy  
 Analysis content : Considering the endpoints, the median and its 95% confidence interval will be calculated using the Kaplan–Meier method. In addition, the Kaplan–Meier curve will be plotted, and the survival

PFIZER CONFIDENTIAL

rate for every 3 months, along with its 95% confidence interval, will be calculated. Greenwood's formula will be used to calculate the confidence interval for the survival rate.

In addition, a frequency table (number of cases, percentage (%)) will be created, considering the event onset, censoring, reasons for the event, and reasons for censoring.

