**【Division of categorical variables】**

Factor	Category
Reasons for the event	Disease progression/adverse event/other (death)/other (excluding death)
Reasons for the censoring	Treatment ongoing; Discontinuation due to efficacy

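### Kaplan-Meier TTD censors efficacy stops, which are a competing event, so the reported rates are neither the share still on treatment nor the share free of a non-efficacy stop

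*SAP*

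**What the plan says.** Protocol 9.3.1.3 measures TTD from the start of the combination "to the end of treatment due to any cause except the effectiveness of the treatment". It does not say how a patient who stops for effectiveness enters the analysis. Protocol 9.7.2 names TTD among the endpoints to be summarised by Kaplan-Meier.

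SAP 5.1 supplies the handling: "In the case of discontinuation due to efficacy, the date of last administration will be used for censoring". The avelumab and axitinib TTDs have the same rule, each using the last dose of that drug. For patients still being treated, "If treatment has not ended, the date of the last hospital visit will be used for censoring".

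Under SAP 7.2.2.6, for all three TTDs, "the median and its 95% confidence interval will be calculated using the Kaplan–Meier method", and the "rate for every 3 months, along with its 95% confidence interval, will be calculated", with Greenwood's formula for the interval. The event reasons are "Disease progression/adverse event/other (death)/other (excluding death)". The censoring reasons are "Treatment ongoing; Discontinuation due to efficacy".

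The visible text contains no cumulative incidence, no analysis in which every stop counts as an event, and no statement of what the censored curve is meant to estimate.

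**The concern.** Censoring suits a patient whose event has not yet been seen but could still occur. A patient on treatment at the last visit fits that description. A patient who has stopped for efficacy does not: the first-line course is over, and it can no longer end through progression, toxicity or death on treatment. Kaplan-Meier handles both patients alike and in effect gives the second the future stopping rate of those still on treatment.

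The resulting curve is the rate that would apply if efficacy stops were removed, and it has that meaning only if the two kinds of stop are independent. That is doubtful, because patients who stop for efficacy are by nature those doing well.

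At stake is what a reader takes from the TTD curve, the median and the 3-monthly rates. Read as the share still on treatment, they are too high. Read as the share that has not had a non-efficacy stop, they are too low.

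**Working it through.** The documents state no TTD rate, median or efficacy-stop frequency, so there is no figure to reproduce. The check has three parts.

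**1. Ten patients, no model.** Invented data: non-efficacy stops at months 3, 8 and 10; efficacy stops at months 6 and 9; five patients on treatment to month 12. At month 11:

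- Kaplan-Meier with efficacy stops censored: 9/10 × 7/8 × 5/6 = 65.6%.
- Still on treatment: 5/10 = 50%.
- Free of a non-efficacy stop: 7/10 = 70%.

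Any earlier efficacy stop puts Kaplan-Meier above the on-treatment share. It falls below the share free of a non-efficacy stop once a non-efficacy stop follows an efficacy stop. With no efficacy stops all three agree.

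**2. Size under assumptions.** Assumed, not in the documents: constant hazards; a median of 12 months for non-efficacy stops, so h1 = ln 2 / 12 = 0.05776 per month; efficacy-stop hazard h2 = r × h1 with r = 0.03, 0.05 or 0.10.

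- Kaplan-Meier as planned: exp(−h1·t)
- Still on treatment: exp(−(1 + r)·h1·t)
- Free of a non-efficacy stop, i.e. 1 minus the cumulative incidence: 1 − [1 − exp(−(1 + r)·h1·t)] / (1 + r)

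For r = 0.10 at t = 24: Kaplan-Meier = exp(−1.386) = 0.250; on treatment = exp(−1.525) = 0.218; free = 1 − 0.782/1.10 = 0.289.

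| r | Kaplan-Meier, 24 months | Still on treatment | Free of a non-efficacy stop | Gaps (points) |
|---|---|---|---|---|
| 0 | 25.0% | 25.0% | 25.0% | 0 and 0 |
| 0.03 | 25.0% | 24.0% | 26.2% | 1.0 and 1.2 |
| 0.05 | 25.0% | 23.3% | 27.0% | 1.7 and 2.0 |
| 0.10 | 25.0% | 21.8% | 28.9% | 3.2 and 3.9 |

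With medians of 9 and 15 months and the same r from 0.03 to 0.10, the 24-month gaps run from 0.8 to 3.5 points (on treatment) and from 0.9 to 5.2 points (free). At r = 0.20 with a 12-month median they are 6.1 and 7.5 points. At r = 0.10 the median is 12.0 months by Kaplan-Meier, 12.0/1.10 = 10.9 months for the share on treatment, and 12.6 months for the share free of a non-efficacy stop.

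A simulation agrees: 150 patients, follow-up uniform from 6 to 34.4 months, 2,000 runs, r = 0.10, about 9 efficacy stops per run. The 24-month means were 24.9% (Kaplan-Meier), 21.7% (on treatment) and 28.8% (free).

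**3. Change over time.** The on-treatment gap in points is largest at t = ln(1 + r)/(r·h1), which is 17.1, 16.9 and 16.5 months for r = 0.03, 0.05 and 0.10. At r = 0.10 it is 3.50 points at 17 months, 3.24 at 24 and 2.50 at 34. Relative to the share on treatment it equals exp(r·h1·t) − 1, which keeps rising: 10.3%, 14.9% and 21.7% at those times. The gap to the share free of a non-efficacy stop rises in points throughout: 2.5, 3.9 and 5.5.

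**The case against.** The strongest reply is that Kaplan-Meier for TTD comes from Protocol 9.7.2. Once efficacy stops are not events, a Kaplan-Meier analysis leads naturally to censoring them, and the SAP mainly supplies the date. This stands. A reader might infer that the SAP departs from the protocol; the documents do not support that.

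A reader might also infer that the protocol's definition is the share free of a non-efficacy stop, so that Kaplan-Meier gets the protocol's own target wrong. That is one reading. Protocol 9.3.1.3 defines a time and an excluded cause and names no target probability; a rate with efficacy stops removed fits Protocol 9.7.2 as well. The understatement is therefore relative to that quantity and is not a breach of the protocol's text.

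A third tempting claim is that both gaps widen with follow-up. In points, only one does.

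On disclosure, the plan tabulates efficacy stops as a censoring reason and as a termination reason for each drug (SAP 7.2.2.7), and adds treatment durations and a swimmer plot. These show how many patients are affected but do not correct the curve, median or rates.

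On size, the gaps at r = 0.03 to 0.10 are smaller than sampling error. With 150 patients, follow-up uniform from 6.1 to 34.4 months and the same 12-month median, the Greenwood 95% half-width at 24 months is about 9 points, or about 11 with 100 patients. The efficacy analysis set is a subset of roughly 150. That stands as a limit on importance, although the displacement is systematic and more patients would not remove it.

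**Conclusion.** The point holds as a matter of estimation and labelling. With efficacy stops censored, the planned TTD curves, medians and 3-monthly rates describe a hypothetical rate under an independence assumption that is neither stated nor likely. They fall between two quantities a reader could name.

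For r of 0.03 to 0.10 and a 12-month median, the 24-month displacement is about 1 to 3 points above the share on treatment and 1 to 4 points below the share free of a non-efficacy stop. The latter gap grows with follow-up. The former peaks at about 17 months in points and afterwards grows only in relative terms. All sizes rest on assumed constant hazards and assumed efficacy-stop frequencies, and are zero if nobody stops for efficacy.

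The effect is probably small. TTD is secondary and descriptive, and no test or sample size depends on it. The improvement is worth making because it is cheap. Redacted parts of the SAP could not be checked for a supplementary TTD analysis.

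**What to change.** In SAP 7.2.2.6, for the combination, avelumab and axitinib TTDs:

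1. Add a Kaplan-Meier curve in which every stop, including a stop for efficacy, is an event, and label it 'still on treatment'.
2. Report the Aalen-Johansen cumulative incidence of non-efficacy stops, with efficacy stop as a competing event, every 3 months with a 95% confidence interval.
3. If the censored curve is kept to match Protocol 9.7.2, label it as the rate with efficacy stops hypothetically removed, and state the independence assumption.

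The cost is SAP wording and a few lines of code. Last-dose dates and reasons for termination are already used in SAP 5.1 and 7.2.2.7, so no new data are needed. Protocol 9.7 lets the SAP modify the protocol's plans and calls for an amendment only for major changes to primary endpoints, which TTD is not. The downside is one extra curve per endpoint.

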### **5.1 EFFICACY/EFFECTIVENESS ENDPOINT(S)**

<Derivation of time-to-event variables>

Item	Derivation method
Real-world progression-free survival (PFS)	Defined as the period from the start date of avelumab plus axitinib combination therapy to

PFIZER CONFIDENTIAL

	
the date of first disease progression (clinical evaluation based on radiographic, clinical, and pathological examinations, as well as other evaluations by the principal investigator or co-investigator) or death from any cause, whichever occurs earlier. If there is no clinical record of death or disease progression, the following dates will be used for censoring, based on medical records:
 
 
(1) If first-line therapy is ongoing, the final progression-free confirmation date or the date of the last hospital visit, whichever is earlier, will be used for censoring.
 
(2) If second-line therapy has not been initiated after the end of first-line therapy, the final progression-free confirmation date or the date of the last hospital visit, whichever is earlier, will be used for censoring.
 
(3) If second-line therapy has been initiated, the date of initiating the second-line therapy will be used for censoring.
 
(4) If nephrectomy has been performed, the date of nephrectomy will be used for censoring.
 

Reasons for real-world PFS events	
Reasons for real-world PFS events are defined as follows:
 
"Disease progression after the initiation of avelumab plus axitinib combination therapy" will be selected if there was disease progression after starting avelumab plus axitinib combination therapy.
 
"Death" will be selected if the patient has died.

Reasons for censoring real-world PFS	
Reasons for censoring real-world PFS are defined as follows:
 
"No disease progression during or after first-line therapy" will be selected if first-line therapy is ongoing or if second-line therapy has not been initiated after the end of first-line therapy.
 
"Second-line therapy started" will be selected if second-line therapy has been initiated.
 
"Nephrectomy performed" will be selected if nephrectomy has been performed.

Overall survival (OS)	
Defined as the period from the initiation of avelumab plus axitinib combination therapy to the date of death from any cause. If there is no

PFIZER CONFIDENTIAL

CT24-WI-GL03-RF03 2.0 *Non-Interventional Statistical Analysis Plan For Secondary Data Collection*  

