**7.2.2.10 Subsequent treatment of avelumab plus axitinib combination therapy**

Source : FAS, Efficacy analysis set

population

Endpoints : Continuous variables

Second-line therapy period (days)

The period from the end date of first-line therapy to the beginning of second-line therapy (days)

Categorical variables

Performance of nephrectomy after avelumab plus axitinib combination therapy

Presence or absence of second-line therapy

Drug category

Second-line therapy regimen by drug category

Analysis : The following aggregation will be performed for the endpoints:  
content Summary statistics will be calculated for continuous variables.  
The period from the end date of first-line therapy to the beginning of second-line therapy (days) will also be estimated, considering the reason for termination of administration.  
A frequency table (number of cases, percentage (%)) will be created for categorical variables.

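### The 13 days added to the last avelumab dose are not cut off at death, so a TTD event can be dated after the patient has died and combination TTD can exceed OS

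*SAP*

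**What the plan says.** SAP 5.1 gives three TTD endpoints, each with its own end date.

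- Combination: "The end date of treatment is the date of last avelumab administration + 13 days or the date of last axitinib administration", and the sentence goes on "whichever occurs later, or the data-cut date, if performed earlier".
- Avelumab: "The end date of avelumab therapy is the date of the last avelumab administration + 13 days or the data-cut date, whichever occurs earlier".
- Axitinib: "The end date of axitinib is the date of the last axitinib administration". Nothing is added.

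None of the three mentions death. The TTD event reasons in SAP 5.1 and 7.2.2.6 are "Disease progression/adverse event/other (death)/other (excluding death"), so a death on treatment is an event. OS is "Defined as the period from the initiation of avelumab plus axitinib combination therapy to the" date of death, and combination TTD starts from the same date.

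Stops for efficacy are censored, but at a different date. For the combination: "In the case of discontinuation due to efficacy, the date of last administration will be used for censoring". The avelumab and axitinib rows say the same for the drug concerned.

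SAP 7.2.2.10 summarises "The period from the end date of first-line therapy to the beginning of second-line therapy (days"). It does not say which end date it means. Protocol 9.3.1.3 defines TTD without the 13 days; Protocol 9.3 leaves detailed definitions to the SAP.

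**The concern.** The added 13 days fit a two-week dosing interval: the last infusion is taken to cover the patient until the next would be due. That is sensible for a living patient, but coverage cannot run past death. The SAP truncates the interval at the data cut and not at death, so some patients would be counted as on treatment after they had died. These dates enter the Kaplan-Meier curves, medians and 3-monthly rates for combination and avelumab TTD. A within-patient check of TTD against OS would flag them as errors.

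A related inconsistency is that two patients with identical dosing dates can have follow-up differing by up to 13 days, only because one stop is recorded as due to efficacy and the other is not.

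**Working it through.** The plan gives no figure to reproduce, so the check applies the SAP's date rules to constructed cases.

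**Inputs**
- Combination end date = min[max(last avelumab + 13, last axitinib), data cut] (SAP 5.1).
- Day count: target − start + 1 if the target is on or after the start; target − start if it is earlier, which is negative (SAP 5).
- 1 month = 30.4375 days (SAP 5).
- Assumption: data cut = 31 October 2022, the end of observation. The SAP uses a data-cut date without giving it. A later cut would limit the excess less often.

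**Death after the last infusion.** Let death fall k days after the last avelumab dose. Axitinib cannot be taken after death, so for k = 0 to 12 the 13-day term always sets the end date. Away from the data cut:

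TTD − OS = 13 − k days.

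With the last avelumab dose on study day 141, the end date is day 141 + 13 = 154 and OS is 141 + k:

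| k | TTD | OS | TTD − OS |
|---|---|---|---|
| 0 | 154 | 141 | 13 |
| 3 | 154 | 144 | 10 |
| 7 | 154 | 148 | 6 |
| 12 | 154 | 153 | 1 |
| 13 | 154 | 154 | 0 |

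The maximum is 13 / 30.4375 = 0.43 month.

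**Near the data cut.** The excess becomes the smaller of 13 − k and the days from death to the cut. With the last avelumab dose on 20 October 2022 and death on 25 October (k = 5), the uncapped end date is 2 November. The cap brings it to 31 October, which is still 6 days after death.

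**Avelumab alone.** The event date is again 13 − k days after death. This clock starts at the first avelumab dose. If axitinib began s days earlier, avelumab TTD − OS = 13 − k − s. Avelumab TTD may then be no longer than OS, but the event is still dated after death.

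**Safeguards.** SAP 6 drops reversed dates only when imputing a partial date caused them. It does not reach these cases.

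**Efficacy stops.** Suppose both drugs are last given on day 0. A stop for efficacy is censored at day 0; any other stop is an event at day 13. For the combination the difference shrinks by one day for each day axitinib continues, and is nil from day 13 (taking last administration to mean the later of the two drugs). For axitinib alone the two dates already agree.

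**With a death cap.** End date = min[max(last avelumab + 13, last axitinib), death, data cut]. TTD − OS is then 0 in every death case tested.

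**Gap to second line, only if SAP 7.2.2.10 uses this end date.** Let second-line therapy start k days after the last infusion, with axitinib already stopped. For k = 1 to 12 the gap is k − 13: −12 days at k = 1, −6 at k = 7, −1 at k = 12. At k = 13 it is 0 + 1 = +1. Counted from the recorded last administration, the k = 7 case gives 7 − 0 + 1 = +8 if axitinib was last taken on the infusion day, or 7 − 6 + 1 = +2 if it was last taken on day 6.

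**The case against.** The 13 days look like a deliberate exposure convention, and the rule already carries a data-cut cap. The study is descriptive and tests no hypothesis. TTD is reported as medians and 3-monthly rates, and no visible analysis compares TTD with OS within a patient. A shift of at most 0.43 month in an unknown subset changes no visible conclusion. This stands as a limit on importance. It does not make an event date after death correct, and the data-cut cap shows that the plan already accepts truncating the interval.

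A reader might go further and infer that negative gaps to second-line therapy, and distorted treatment durations in SAP 7.2.2.7, are established. They are not. The starred definition sits inside the TTD rows, and neither 7.2.2.7 nor 7.2.2.10 refers to it. Much of the SAP between 5.2 and the categorical derivations is blacked out and may hold separate derivations. If the gap runs from the recorded last dose, the 13-day rule produces no negative value. Nor can one say that the gap summary suffers more than TTD: the documents give neither the distribution of gaps nor the number of early switches.

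One might also read the efficacy-stop rule as a different clock for every endpoint. It differs only for combination and avelumab TTD, and it is a separate inconsistency from TTD exceeding OS.

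**Conclusion.** The rule is wrong as written for combination and avelumab TTD: a death 0 to 12 days after the last infusion produces a TTD event dated up to 13 days after death. This follows from the visible text. The assumed data-cut date affects only how often the existing cap shortens the excess.

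The point is minor. Only some event times move, each by no more than 0.43 month, so the effect on median TTD is small. A 3-monthly rate is affected only where a landmark falls between a patient's death and the derived end date. How many patients die within this window is not stated.

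The negative-gap point is conditional on 7.2.2.10 using the TTD end date. Whether treatment duration is affected cannot be judged from the visible text.

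**What to change.** 1. In SAP 5.1, cap the derived end date for combination and avelumab TTD at the date of death as well as at the data-cut date. Axitinib TTD needs no change.
2. For the same two endpoints, censor efficacy stops at the same derived end date (last avelumab + 13 days where that applies, with the same caps), so that follow-up does not depend on the recorded stop reason.
3. In SAP 7.2.2.10, state that the gap runs from the recorded last administration of first-line therapy, not from the date with 13 days added.

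For item 3, capping the end date at the day before second-line start is a poor substitute. Under the SAP's day count it gives k − (k − 1) + 1 = +2 days for every capped patient, so a switch 1 day and a switch 12 days after the last infusion would look the same. It could also override a recorded axitinib administration on or after second-line start.

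The cost is SAP wording and a few lines of programming. OS, TTD and 7.2.2.10 already need the dates involved, and no patient's treatment is affected.
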